16.3 The query process

The Monitor will review the eCRFs and evaluate them for completeness and consistency. Data in the eCRF will be compared with the respective source documents to ensure that there are no discrepancies for critical data as described in the RBM plan. All entries, corrections, and alterations are to be made by the Investigator or designee.

CONFIDENTIAL 54(64)

If corrections are needed, queries will be raised within the eCRF, either as a result of built-in edit checks or manually raised by the Monitor. An appropriate member of the site staff will answer the queries in the eCRF either by correcting the data or by entering a response to the query.

16.4 Audit trail

All entries in the eCRF will be fully recorded in a protected audit trail. Once clinical data have been saved, corrections to the data fields will be audit trailed, meaning that the reason for change, the name of the person who made the change, together with time and date will be logged.

16.5 External data

External data consists of data that are not recorded in the eCRF. Data may be received in electronic format or as a paper printout. Key variables are defined in order to uniquely identify each sample record. File and data formats are agreed with the external data provider.

16.6 Medical coding

Medical coding will be performed by trained personnel at CTC. AEs and medical/surgical history verbatim terms are coded using the medical dictionary of regulatory activities (MedDRA, latest version available at eCRF setup).

Prior and concomitant medications will be coded according to the WHO anatomic therapeutic chemical (ATC) classification system. All coding will be approved by the Sponsor prior to database lock.

16.7 Database lock

When all data has been entered and discrepancies solved, clean file will be declared, the database will be locked, and the data will be analyzed.

CONFIDENTIAL 55(64)

17 STATISTICAL METHODS AND DETERMINATION OF SAMPLE SIZE

The principal features of the statistical analysis to be performed are described in this section. A more technical and detailed elaboration of the principal features will be presented in a separate statistical analysis plan (SAP), which will be signed and approved prior to database lock.

17.1 General

Continuous data will be presented in terms of evaluable and missing observations, arithmetic mean, standard deviation (SD), median, minimum, and maximum value, Q1-Q3 (interquartile range [IQR]).

Categorical data will be presented as counts and percentages. When applicable, summary data will be presented by IP, and by assessment time. Individual subject data will be listed by subject number, IP, and, where applicable, by assessment time.

All descriptive summaries and statistical analyses will be performed using SAS Version 9.4 or later (SAS Institute, Inc., Cary, NC). The PK parameters will be calculated by non-compartmental analysis using the software Phoenix WinNonlin® version 8.3 or later (Certara, U.S.A.).

Baseline will be defined as the last data collection point prior to each IP administration.

No adjustment for multiple comparisons will be performed. All formal comparisons will be made towards a designated reference product and all significant findings will be reviewed for medical relevance.

17.1.1 Missing, unused and spurious data

Generally, no imputation of data will be performed. In case of missing start and stop times of AEs that cannot be investigated further, missing data will be imputed according to a worst-case scenario, *i.e.*, start time will be imputed as the closest time point post intake of IP and end time as 23:59, resulting in the longest possible treatment emergent duration of the AE.

Spurious data will be evaluated continuously through data validation (see Section 16) and, if connected to protocol deviations, evaluated case-by-case at the latest prior to declaration of clean file and database lock.

Deviations from the original SAP will be described in the CSR.

[figure not shown]
Methods for handling of missing, unused, and spurious data will be further specified in the SAP.

17.2 Determination of sample size

About 66 subjects will be screened to achieve 36 randomized subjects and 32 fully evaluable subjects. A fully evaluable subject is defined as a subject who has received all 11 IPs and who has completed all study visits. An effort will be made to randomize at least 14 female subjects (approximately 40 %).

The sample size has been calculated considering the secondary endpoint: to show equivalence between the unflavored NP 6 mg and flavored NP 6 mg products. A lower number of subjects will be needed for the primary endpoint. Using a CV of 29 %, based on previous studies, a power of 80 %, a significance level of 10 %, lower and upper equivalence bounds of 0.8 and 1.25, and a null ratio of 1, 32 evaluable subjects will be needed. Assuming a dropout rate of 10 %, a total of 36 subjects will be randomized.

CONFIDENTIAL 56(64)

17.3 Analysis data sets

17.3.1 Full analysis set

The Full Analysis Set (FAS) will consist of all subjects who have been randomized and received at least 1 IP administration and who have at least 1 post-baseline data point. This population will be used for the safety analysis set.

17.3.2 PK analysis set

The PK analysis set (PKAS) will consist of all subjects who received at least 1 IP administration and provided at least 1 evaluable PK-profile and no major deviation or AEs judged to compromise the PK analysis. Individual PK values and/or full profiles for explicit IPs may be excluded from the analysis as specified in the SAP.

17.4 Pharmacokinetic analysis

The PK analysis will be based on the PKAS and performed by CTC. The PK parameters will be calculated by non-compartmental PK analysis using the software Phoenix WinNonlin® version 8.3 or later (Certara Inc, Princeton, New Jersey, U.S.A.). In addition to AUC_{0-inf} and C_{max} parameters, other non-compartmental PK parameters will be determined in relation to secondary endpoints (see Section 17.7.2 below). Where possible, both baseline-adjusted and non-adjusted PK parameters will be calculated.

For AUC_{0-inf} , the area under the plasma concentration vs. time curve will be calculated to the time point of the last quantifiable plasma concentration of nicotine and then extrapolated to infinity using the concentration in the last quantifiable sample and the estimated terminal elimination rate constant (Lambda_z).

PK data will be presented for each IP using summary statistics. This data will be presented in terms of N, arithmetic mean, median, SD, minimum and maximum value. For AUC and C_{max} parameters, the geometric mean and CV % will be presented. Categorical data will be presented as counts and percentages, as applicable.

17.5 Description of study population

17.5.1 Demographics and baseline characteristics

Descriptive statistics for demographics, weight and height, BMI as well as history of oral tobacco/nicotine use, and smoking will be presented for all subjects. All data will be listed by subject number.

17.5.2 Medical/surgical history and prior/concomitant medication

Medical/surgical history will be presented by system-organ-class (SOC) and preferred term (PT). Prior/concomitant medications will be presented by ATC level 4 and 5. All data will be listed by subject number.

17.5.3 Treatment compliance

The number of subjects treated with each IP will be presented through listings.

CONFIDENTIAL 57(64)

17.5.4 Physical examination

Physical examination parameters will be specified as "normal", "abnormal, not clinically significant", or "abnormal, clinically significant (as judged by the Investigator at the screening visit) and summarized.

All data will be listed by subject.

17.5.5 Vital signs

Vital signs (systolic/diastolic blood pressure, pulse rate) will be summarized by IP. If applicable, data will be presented with absolute and percent change from baseline.

All data will be listed by subject.

17.5.6 Electrocardiogram

All ECGs will be categorized as" normal"," abnormal, not clinically significant", or" abnormal, clinically significant" (as judged by the Investigator at the screening visit) and summarized.

All data will be listed by subject.

17.6 Analysis of primary endpoint

17.6.1 Comparison of the new format unflavored NP 6 mg and comparator ($AUC_{\theta-inf}$)

The primary endpoint of this study is to compare nicotine exposure, as measured by baseline-adjusted AUC_{0-inf} based on nicotine plasma concentrations, between the new format unflavored NP 6 mg product and the comparator product, Longhorn Natural 18 mg.

AUC_{0-inf} will be calculated as described in Section 17.4 above.

The comparison of AUC_{0-inf} between the new format unflavored NP 6 mg and the comparator Longhorn Natural 18 mg will be assessed using the following null (H₀) and alternative (H₁) hypotheses:

$$H_0: \frac{\mu_T}{\mu_R} \ge 1.25$$

$$H_1: \frac{\mu_T}{\mu_P} < 1.25$$

where μ_T is the least-squares geometric mean of $AUC_{0\text{-inf}}$ for the new format unflavored NP 6 mg and where μ_R is the least-squares geometric mean of $AUC_{0\text{-inf}}$ for the comparator Longhorn Natural 18 mg.

In the analysis, a mixed model will be used with the natural log of AUC_{0-inf} as the dependent variable, treatment as a fixed effect and subject as a random effect. The improved Kenward-Roger's approximation for degrees of freedom will be used. The estimated least-squares means (LSMeans) difference between the new format unflavored NP 6 mg and the comparator Longhorn Natural 18 mg will be back transformed into the original scale to present the ratio of geometric LSMeans as well as the corresponding 90 % confidence interval. If the upper bound of the 90 % confidence interval of this ratio is below 1.25, the null hypothesis will be rejected, and it will be concluded that the new format unflavored NP 6 mg product does not result in substantially higher nicotine exposure compared to the comparator product. The model will be estimated for both non-adjusted and baseline-adjusted AUC_{0-inf}.

CONFIDENTIAL 58(64)

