8.1 Overall study design and schedule of events

This is a multi-center, open-label, randomized, 11-way cross-over, single dose administration study, designed to assess nicotine exposure from new format NP products. The IPs include 2 unflavored products (3 mg and 6 mg) and 8 flavored products (Flavor A-H 6 mg). The comparator product is Longhorn Natural 18 mg.

The study will include 36 randomized subjects with the aim of achieving 32 evaluable subjects. The subjects are healthy male or female oral tobacco/nicotine pouch users aged 21 to 60 years, inclusive, who have used oral tobacco/nicotine products for ≥1 year, with a minimum daily consumption of 5 or more pouches. An effort will be made to randomize at least 14 female subjects (approximately 40%). Each subject will participate in the study for approximately 5 weeks, not including the preceding 4-week screening period.

An overview of the study design is shown in Figure 8.1-1.

Figure 8.1-1 Overview of the study design

Subjects will report to the study sites for a screening visit (Visit 1) followed by 11 treatment visits (Visits 2-12) on separate days. Screening will take place within 4 weeks prior to Visit 2 and will include an eligibility check, including evaluations of smoking and oral tobacco/nicotine use, a brief physical examination, serology tests, electrocardiogram (ECG) and collection of medical history, vital signs (pulse rate and blood pressure), height, weight, and body mass index (BMI) and a product familiarization session. For details, refer to Table 8.1-1.

At the end of the screening visit, the subjects will complete a product familiarization session. During this session, they will be provided with the comparator product, Longhorn 18 mg nicotine, to ensure the acceptability of the product. The subjects will use the product in the same way they would normally use a snus or NP product (*i.e.*, placing it under the upper lip). The duration of product use will be a minimum of 20 minutes, starting from the moment the subject places it in their mouth until they remove it. Subjects who successfully complete this familiarization session, tolerating the product without significant unexpected adverse effects, will be allowed to continue in the study.

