9.9 Randomization

At Visit 2, subjects will be randomized to one of 11 administration sequences. As this is an open-label study, the IP administration sequence to which each subject is allocated will be recorded in the eCRF. Computer-generated randomization lists for each site will be created using the statistical analysis software (SAS) Proc Plan, SAS Version 9.4. The randomization lists will contain site, subject number, randomization sequence, day, and product.

The randomization list will be generated by CTC. The original randomization list will be kept by the randomizer and copies of the randomization list will be provided to each site and to the IP packing company.

CONFIDENTIAL 34(64)

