17.7.2 Pharmacokinetics of nicotine in plasma

The following non-compartmental PK parameters will be determined for each IP: AUC_{0-inf} , AUC_{0-last} , $AUC_{0-l.5h}$, C_{max} , T_{max} and $T_{1/2}$. Where possible, both baseline-adjusted and non-adjusted PK parameters will be calculated.

 C_{max} and T_{max} will be derived from the observed nicotine plasma concentration data. AUC_{0-1.5h} and AUC_{0-last} will be calculated using log-linear trapezoidal interpolation. Calculations will be based on the actual sampling times recorded during the study. Concentrations below the lower limit of quantification (LLOQ) occurring before C_{max} will be treated as zero. Concentrations below LLOQ occurring after C_{max} will be omitted from the analysis. All baseline-adjusted PK parameters will be corrected for nicotine plasma concentrations at baseline (preadministration).

AUC_{0-inf} will be calculated as described in Section 17.4 above.

The equivalence in $AUC_{0\text{-inf}}$ and C_{max} between the unflavored NP 6 mg and each flavored NP 6 mg will be assessed using a mixed model with the natural log of AUC_{inf} as the dependent variable, treatment as a fixed effect and subject as a random effect. The improved Kenward-Roger's approximation for degrees of freedom will be used. The estimated LSMeans difference between unflavored NP 6 mg and flavored NP 6 mg will be back transformed into the original scale to present the ratio of geometric LSMeans as well as the corresponding 90 % confidence interval. If the 90% confidence interval of this ratio falls within the range 0.8-1.25, the IPs will be considered equivalent. The model will be estimated for both non-adjusted and baseline adjusted $AUC_{0\text{-inf}}$.

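### The primary and equivalence models omit period in an 11-period cross-over that cannot be exactly balanced: the tests stay valid, but a visit trend would cost precision that one model term recovers

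*Protocol*

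**What the plan says.** Section 8.1 describes a "multi-center, open-label, randomized, 11-way cross-over, single dose administration study", with 11 treatment visits (Visits 2 to 12) over about five weeks. Under section 9.9, "subjects will be randomized to one of 11 administration sequences", and "Computer-generated randomization lists for each site will be created". The protocol does not say how the 11 sequences are built or whether the lists are blocked.

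Section 17.2 states: "About 66 subjects will be screened to achieve 36 randomized subjects and 32 fully evaluable subjects". It allows for 10% dropout. Section 17.3.2 keeps subjects with as few as one evaluable PK profile and lets single profiles be excluded.

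The primary model in 17.6.1 has the log of AUC0-inf as response, with "treatment as a fixed effect and subject as a random effect". The equivalence model in 17.7.2 takes the log PK parameter "as the dependent variable, treatment as a fixed effect and subject as a random effect". Neither section mentions period, visit or sequence, and nothing else in section 17 adds them. Section 8.2 deals with carryover through 12 hours of abstinence and says nothing about trends over visits.

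**The concern.** Period is a design factor of a cross-over. A model with treatment and subject only removes visit effects from the product ratios exactly if each product occurs equally often at each visit and the data are complete. Even then, the visit effects stay in the residual. Here exact balance is not attainable, so any trend over the visits does two things. It adds a chance error to each ratio, depending on the realised allocation, and it inflates the residual variance, which widens every 90% interval. What is at stake is precision for the primary comparison against 1.25 and for the eight flavour comparisons against 0.80-1.25.

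**Working it through.** **Inputs.** From 17.2: 36 randomised, 32 evaluable, 10% dropout, bounds 0.80 and 1.25, true ratio 1, "Using a CV of 29 %, based on previous studies", and "a power of 80 %, a significance level of 10" per cent, read as 5% per side to match the 90% interval. From 9.9: 11 sequences, one list per site. Assumed, because the protocol does not give them: the CV is within-subject; drift is linear on the log scale from first to last visit; the sequences form a Latin square; lists are blocked unless stated otherwise.

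**1. The plan's own figure.** The log-scale variance is ln(1 + 0.29^2) = 0.0807, so the SD is 0.284. The two one-sided tests need 30 subjects for 80% power with n - 2 degrees of freedom; power at 32 is 0.846. Using 0.29 directly as the log-scale SD gives 31. The stated 32 is therefore reproduced within two subjects, and 32/0.9 = 35.6 gives 36. Reading 10% as the level per side would give 23, which does not match.

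**2. Balance.** 36 = 3 x 11 + 3 and 32 = 2 x 11 + 10. Neither fills 11 sequences equally; 33 or 44 would.

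**3. Residual inflation.** For a total log-scale drift L over 11 equally spaced visits, the variance of the visit effects is 0.11 L^2 (squared deviations of 0, 0.1, ..., 1 sum to 1.1; divide by 10). The relative inflation is 0.11 L^2 / 0.0807, and the standard error grows by the square root of one plus that.

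| Total drift | 0.11 L^2 | Residual variance | Standard error |
|---|---|---|---|
| 10% rise / fall | 0.0010 / 0.0012 | +1.2% / +1.5% | +0.6% / +0.8% |
| 20% rise / fall | 0.0037 / 0.0055 | +4.5% / +6.8% | +2.2% / +3.3% |
| 30% rise / fall | 0.0076 / 0.0140 | +9.4% / +17% | +4.6% / +8.3% |

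A fall costs more than a rise of the same percentage because ln 0.7 is larger in size than ln 1.3.

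**4. Chance shift in a ratio.** Over simulated blocked allocations with 32 of 36 subjects, the 95th percentile of the shift in a pairwise ratio is about 1.5-2% for a 20% drift and about 2-3% for a 30% drift. For rises of 10, 20 and 30%, the SD of the shift is 0.003, 0.006 and 0.009 on the log scale. The standard error of a difference is 0.284 x sqrt(2/32) = 0.071. If the sequences were drawn without blocking (36 complete subjects), the SD is 0.014 for a 20% rise and 0.020 for a 30% rise.

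**5. Error rate and power without the period term.** At a true ratio of 1.25 the simulated one-sided type I error is 5.1% with no drift, 4.4% with a 20% fall and 3.9% with a 30% fall. With unblocked sequences it is 5.1% and 5.0% under the same two falls. At a true ratio of 1 with 32 subjects, equivalence power is 86.4% with no drift, about 84% with a 20% drift either way, about 82% with a 30% rise and about 79% with a 30% fall. That calculation treats the inflated residual as true error. A simulation with blocked lists gives 81.3% for the 30% fall, because near-balance widens the interval more than it scatters the estimate. Primary power stays at about 89% or above.

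**6. Price of the period term.** Residual degrees of freedom go from 10 x 31 = 310 to 300, and equivalence power from 0.8636 to 0.8635. Because period and treatment are not quite orthogonal, the variance of a contrast also rises by about 0.2% with 36 subjects and 0.5% with 32 (1.1% at most in simulation). Setting 0.11 L^2 / 0.0807 = 0.005 gives L = 0.061, so on interval width the term breaks even at a drift of about 6%. Below that, gain and cost are both trivial.

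**The case against.** A reader might infer that the primary ratio and the flavour ratios are biased, or that the trial could wrongly pass the 1.25 limit. The documents do not support that. Order is randomised, so the shift has expectation zero over allocations, and the wider interval pays for it: the type I error in step 5 does not exceed its nominal level beyond simulation error.

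Nothing in the protocol points to a drift of 20-30%. Entrants have used oral products for at least a year at five or more pouches daily, there is a familiarisation session (with the comparator only), those intending to change their nicotine habit are excluded, and the primary parameter is baseline-adjusted. Whether assay batches line up with visits is not stated. With a drift of 10% or less the effect is negligible. All of this stands and limits the size of the point.

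It can also be said that section 17 gives only principal features and leaves detail to the SAP. That is a partial answer at best. The protocol writes out the model terms for the primary and equivalence tests, so an SAP that follows it will omit period.

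Nor do the documents show that a sequence term is required. The period term is what corrects for visit imbalance.

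**Conclusion.** The point holds as a matter of efficiency. The protocol fixes a model without period for an 11-period cross-over whose planned numbers cannot be balanced over 11 sequences. The analysis as written is valid, and slightly conservative if the lists are blocked. What it risks is wider intervals and a small chance error in each ratio. Under the stated assumptions this ranges from under 1% on the standard error at 10% drift to 4.6-8.3% at 30% drift. Only a fall of about 30% brings equivalence power near or just below the planned 80%. These figures rest on an assumed linear drift, Latin square and blocking, none of which the protocol states. The sample size is not called into question.

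**What to change.** In 17.6.1 and 17.7.2, add period (Visits 2 to 12) as a fixed effect beside treatment, keep subject random and keep the Kenward-Roger degrees of freedom. State that the same model applies to ln(AUC0-inf) and ln(Cmax), since 17.7.2 announces both parameters but names only AUC as the response. Sequence may be added if the sponsor prefers, but this correction does not need it.

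The cost is one line in each section, carried into the SAP. The randomisation list already holds day and product for each subject, so no new data are needed, and 32 evaluable and 36 randomised can stay. The change should be made before database lock, because in an open-label study a period term added after the results are seen would be a post hoc choice of model.

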17.7 Analysis of secondary endpoints

17.7.1 In vivo extracted amount and fraction of nicotine

The difference between the nicotine content of an unused reference pouch and the used study pouch will be used to calculate the *in vivo* extracted amount of nicotine for each IP. The mean of the extracted amount (mg/unit) and extracted fraction (%) of nicotine between unflavored NP 3 mg, the unflavored NP 6 mg and flavored 6 mg products and the comparator product Longhorn Natural 18 mg will be calculated. The amount of nicotine in the reference pouches and in used pouches will be presented through descriptive statistics.

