The new format NP product offers a smaller pouch size and contains a reduced amount of nicotine compared to currently available ZYN Slim products on the Swedish market. In accordance with FDA regulations, the new format NP product will be subjected to comparative testing against a tobacco product within the same category and currently available on the US market. The tobacco product in this study is the US moist snuff Longhorn Natural 18 mg, previously used in another clinical study, and for which only around 5.4 mg of the nicotine was found to be released after 60 minutes of usage. The current study will investigate the nicotine delivery and uptake profile of the new format NP, including 2 unflavored products (3 mg and 6 mg) and 8 flavored products (6 mg) in comparison with Longhorn Pouch Natural 18 mg.

The results from this study are intended to be used as a basis in a premarket tobacco product application to the FDA. Prior to introduction and marketing of novel nicotine-based products in the US, the FDA specifically requires data on nicotine uptake and nicotine effects in order to assess health risks and addiction potential of the new tobacco/nicotine-containing products as compared to existing ones.

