Subjects shall abstain from tobacco/nicotine products as well as smoking (cigarettes or ecigarettes) for 12 hours prior to each treatment visit (Visits 2-12). All treatment sessions will be performed during the morning hours (08:00 to 12:00) to facilitate abstinence.

The IPs will be administered as single pouches in a pre-determined randomized order. Subjects will keep the pouch still between the upper lip and gum for 30 minutes and will be instructed not to manipulate the pouch with the tongue or lips. They will also be instructed not

CONFIDENTIAL 25(64)

to eat, drink, chew gum, or brush their teeth for 30 minutes before, during, or 30 minutes after IP administration.

After 30 minutes, each used pouch will be collected and frozen (-20°C) pending analysis of residual nicotine content. Unused pouches from the same batch will serve as references and will be stored at -20°C pending analyses.

Blood samples for the assessment of nicotine plasma levels and PK parameters will be collected at pre-defined time points from pre-administration to 6 hours after each IP administration. The PD effects of the IPs will be determined using pulse rate measurements and subjective parameters (using VAS questions) at the same pre-defined time points as well as a MCQ 30 minutes after IP administration.

AEs will be collected through subject interviews and will also include any AEs reported spontaneously by the subjects, starting from the initiation of IP administration (Visit 2), and continuing until the last treatment visit (Visit 12). An overall schedule of event is presented in Table 8.1-1 and a detailed schedule of events for each treatment visit is presented in Table 8.1-2. Study assessments are described in Section 11.

CONFIDENTIAL 26(64)

Table 8.1-1 Schedule of events

Events	CSP section	Visit 1 Screening	Visit 2 First treatment visit	Visits 3-12 Treatment visits
Informed consent	11.2.1	X		
Demographics	11.2.2	X		
Medical/surgical history	11.2.3	X		
History of nicotine use	11.2.4	X		
Inclusion/exclusion criteria	9.4/9.5	X	X ¹	
Weight, height, and BMI	11.2.6	X		
Physical examination	11.2.7	X		
Vital signs (blood pressure and pulse rate)	11.2.8	X		
Electrocardiogram	11.2.9	X		
HIV, Hepatitis B and C	11.2.10	X		
Product familiarization session	11.2.11	X		
Pregnancy test ²	11.2.12	X	X	X^3
Urine drug screen ⁴	11.2.13	X	X	
Alcohol screen ⁴	11.2.14	X	X	
Randomization	9.9		X	
IP (pouch) administration	10.5		X ⁵	X ⁵
PK blood sampling (plasma)	11.3.1		X ⁵	X ⁵

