10.2 Manufacturing, packaging, and labelling

All IPs are manufactured and packaged by Swedish Match in compliance with the Swedish law on food production. Production sites and batch IDs for the IPs will be documented in the trial master file (TMF).

IPs will be transferred from the original container, weighed, and individually packaged in identical sealed food approved test containers at the Swedish Match analytical laboratory. The containers will be labelled with unique identification numbers by Swedish Match in accordance with the randomization lists. IPs will be shipped by Swedish Match directly to CTC.

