10.3 Conditions for storage

IPs will be stored in access-controlled storage areas at the study sites under refrigerator temperature (4-8°C).

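### The extraction formula in section 17.7.1 has no term for each study pouch's own weight, although the pouches are weighed; this costs precision in the extraction endpoints

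*Protocol*

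**What the plan says.** Section 17.7.1 gives the rule: "The difference between the nicotine content of an unused reference pouch and the used study pouch will be used to calculate" the extracted amount for each product. Means of extracted amount (mg/unit) and extracted fraction (%) are then reported by product. Section 8.1 identifies the references: "Unused pouches from the same batch will serve as references". The number of reference pouches is not given.

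Section 10.2 describes the preparation of the products: "IPs will be transferred from the original container, weighed, and individually packaged in identical sealed food approved test containers", with a unique identification number on each container. The protocol states no use for the weights.

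On scale, section 8.1 states: "The comparator product is Longhorn Natural 18 mg". Section 6.1 reports that in an earlier study of this product "only around 5.4 mg of the nicotine was found to be released after 60 minutes of usage". In the present study each pouch is used for 30 minutes.

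On storage, section 10.3 keeps the study pouches at 4-8 °C. Section 8.1 says of the unused reference pouches that they "will be stored at -20°C pending analyses", without saying when they go into the freezer.

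**The concern.** Subtracting a used pouch's residual from a reference content treats every pouch of a batch as if it started with the same amount of nicotine. A pouch filled slightly light then appears to have released more than it did, and a heavy one less. The comparator's extracted amount is a modest difference between two larger quantities, so a small percentage error in starting content becomes a larger percentage error in the result.

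Extracted amount and fraction are secondary endpoints 1 and 4. Each subject's extracted amount also bears on the exploratory extraction-normalized AUC and Cmax (section 17.8.2). The measurement that would remove most of this noise appears to be taken already.

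**Working it through.** **Inputs from the protocol.** Content C = 18 mg (comparator) and 6 mg (nicotine pouch). Comparator extraction of about 5.4 mg after 60 minutes gives f = 5.4/18 = 30%. There are 32 evaluable subjects, hence 32 pouches per product. The protocol states no precision for the extraction endpoints, so there is no figure of its own to reproduce.

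**Inputs assumed.** c, the pouch-to-pouch CV of content due to fill weight, is taken as 2-5%. The extracted fraction of the nicotine pouches is not given, so a range is shown.

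**Error in one study pouch.** Let the true content be C(1+e), where e has mean zero and SD c.
- Residual: C(1+e)(1−f).
- Calculated amount: C − C(1+e)(1−f).
- True amount: C(1+e)f.
- Error in amount: C − C(1+e) = −C·e, with SD C·c, whatever f is.
- Relative to the extracted amount: c/f.
- Error in the extracted fraction: −e(1−f), with SD c(1−f).

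| Product | f | SD, mg (c = 2% to 5%) | SD as % of extracted amount | SD of fraction, points |
|---|---|---|---|---|
| 18 mg | 30% | 0.36 to 0.90 | 6.7 to 16.7 | 1.4 to 3.5 |
| 6 mg | 30% (assumed) | 0.12 to 0.30 | 6.7 to 16.7 | 1.4 to 3.5 |
| 6 mg | 45% (assumed) | 0.12 to 0.30 | 4.4 to 11.1 | 1.1 to 2.75 |
| 6 mg | 60% (assumed) | 0.12 to 0.30 | 3.3 to 8.3 | 0.8 to 2.0 |

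A simulation for the 18 mg pouch at c = 5% gave a mean error of 0.000 mg and an SD of 0.90 mg, in agreement with the algebra.

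**Effect on a product mean.** The added standard error is C·c/√32. For the comparator this is 0.36/5.66 = 0.06 mg to 0.90/5.66 = 0.16 mg, or 1.2% to 2.9% of 5.4 mg. For a 6 mg product it is 0.02 to 0.05 mg.

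**Error in the reference.** If the reference is the mean of n pouches, its weight-driven error has SD C·c/√n and enters every subject's value for that product and batch with the same sign. For the comparator:

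| Reference pouches (assumed) | c = 2% | c = 5% |
|---|---|---|
| 1 | 0.36 mg | 0.90 mg |
| 3 | 0.36/√3 = 0.21 mg | 0.90/√3 = 0.52 mg |
| 10 | 0.36/√10 = 0.11 mg | 0.90/√10 = 0.28 mg |

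At c = 5%, even ten reference pouches leave a shared error (0.28 mg) larger than the added standard error from 32 study pouches (0.16 mg).

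**Storage, as an illustration only.** If study pouches lost a share L of their nicotine before use and the references did not, the error in amount would be C·L. At an assumed L = 2% that is 0.36 mg for the comparator and 0.12 mg for a 6 mg pouch.

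**The case against.** The strongest reply is that the omission is an inference from silence. Section 17.7.1 is a summary, the introduction to section 17 leaves technical elaboration to the SAP, and weighing at the sponsor's own analytical laboratory fits a planned weight correction. A reader might infer that the plan has decided to discard the weights. The documents do not support that: nothing rules a correction out. It remains true that 17.7.1 states the calculation itself, without a weight term and without the express referral to the SAP that 17.7.3 makes for pulse rate.

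Second, random weight error averages out. This stands for the study pouches, and extraction is reported only as means and descriptive statistics. It does not hold for error in the reference, which is shared across subjects.

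Third, a reader might infer that the error falls hardest on the comparator. In mg it is three times larger (18/6), provided the weight CVs are equal. In relative terms it is larger only if the nicotine pouches release a greater fraction than the comparator's roughly 30%, and the protocol gives no such figure.

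Fourth, a reader might infer from 4-8 °C against -20 °C that extraction is overstated. That is not shown: the references may be refrigerated with the study pouches first, the containers are sealed, and no loss rate is given. Even with an equal proportional loss, the added mg would cancel between the 6 mg products (objective 4), and a 30-point difference in extracted fraction would shrink only to 30 × 0.98 = 29.4 points.

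**Conclusion.** The point holds as a matter of precision. As written, the formula counts fill-weight variation as extraction. The per-pouch figures above rest on an assumed weight CV of 2-5%, on content varying in proportion to weight and, for the comparator's relative error, on the 30% seen after 60 minutes. If 30 minutes of use releases less, that relative error is greater.

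The more important part is the reference. Its sampling error is common to all subjects for a product, and neither its size nor the number of reference pouches can be read from the protocol. A storage bias is possible but not demonstrated.

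The effect is confined to the precision of secondary endpoints 1 and 4 and to the exploratory normalized AUC and Cmax, which may not appear in the study report. The primary endpoint, plasma AUC from zero to infinity, does not use extraction and is unaffected. This is a worthwhile improvement, not a threat to the trial's main conclusion.

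**What to change.** In section 17.7.1, define for each used pouch:

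- starting content = mean nicotine concentration of its batch (mg/g, from the unused reference pouches) × that pouch's recorded pre-use weight;
- extracted amount = starting content − measured residual;
- extracted fraction = extracted amount / starting content.

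This removes the weight-driven part of both the study-pouch and the reference error. Assay error and pouch-to-pouch differences in concentration remain, so the number of reference pouches per batch should also be stated.

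In the handling instructions, keep the reference pouches with the study pouches at 4-8 °C and freeze them alongside the used ones. Any storage loss before use then applies equally to both.

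The cost is small. The reference pouches must be weighed, the study-pouch weights must be recorded against the unique container numbers, and both must be transferred to the analysis data. If the SAP or the laboratory method already specifies this correction, a cross-reference in 17.7.1 is enough.
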